12.3 Data Management Responsibilities

Data collection is the responsibility of the study staff at the site under the supervision of the site Principal Investigator. During the study, the Investigator must maintain complete and accurate documentation for the study.

Data management and oversight is the responsibility of the Sponsor or Sponsor Representative. Responsibilities include, but are not limited to, the following:

- Clinical strategy and oversight
- Clinical study operations
- File management and study documentation
- Site initiation visits and study close-out visits
- Clinical quality assurance
- Statistical support and programming
- Data management, including database development and programming and electronic data capture (EDC) programming, training, and management

Additionally, management and oversight of photographic imaging is the responsibility of the Sponsor.

Responsibilities may be delegated to applicable vendors.

12.4 Data Capture Methods

Data will be recorded on Paper Data Capture forms, then transcribed into an Electronic Data Capture (EDC) system and saved in that system as an electronic case report form (eCRF).

Photographic images will be captured utilizing the Canfield Scientific Vectra M4 Plus 3D Imaging system as specified in the Canfield User Manual for the study.

APPENDIX A: SAMPLE SUBJECT SATISFACTION SURVEY

Subject Satisfaction Survey

1. Are you happy with the results of the procedure performed?
 YES NO
2. What types of changes to you notice from the results of the procedure performed?

(Check all that apply)

- More jawline definition
- Reduction in jowls
- Improvement in skin texture in the treatment area
- Reduction in the area under the chin
- Reduction of lines & wrinkles in the treatment area
- Other changes noticed *(please list):*

3. Would you recommend the procedure performed to a friend?
 YES NO
4. Would you consider having the same type of procedure performed on another part of your body?
 YES NO
5. On a scale from 1-10 (1 is the worst, 10 is the best), what is your overall satisfaction with the procedure and the results of the procedure performed?

1 2 3 4 5 6 7 8 9 10

Worst *(circle ONE number)* *Best*

APPENDIX B: SAMPLE STUDY SUBJECT DAILY DIARY*To be completed by study staff:*

Site ID #	Subject ID	Subject Initials	Procedure Date		
					
			First/Middle/Last	Day	Month
					Year

Instructions to subjects:

Please use this form to record any complications after your study procedure. Be sure to complete an entry every day until your 14-day follow-up visit. Please bring this form to your 14-day follow-up visit.

Day X	Date:										
Please rate the average pain you are experiencing in the treatment area on a scale of 0-10, with 0 being 'Best/No Pain' and 10 being the 'Worst Possible Pain'. Please check one box.											
	0	1	2	3	4	5	6	7	8	9	10
Pain											
Please check all boxes that apply to record any expected treatment effects that you are experiencing.											
Expected Treatment Effect	Are you experiencing this event?					Is this causing an impact to your daily activities such as work, sleep, driving, appetite, etc.?					
Swelling		YES		NO			YES		NO		
Redness of the skin		YES		NO			YES		NO		
Bruising		YES		NO			YES		NO		
Touch sensitivity, numbness/tingling, itching		YES		NO			YES		NO		
Firm areas under the skin		YES		NO			YES		NO		
Crackling sound or popping feeling under the skin		YES		NO			YES		NO		
Are there any other complications you are experiencing?	 YES*  NO *If "YES", please call your study doctor to discuss.										
Are you wearing your compression garment 22 hours/day for Days 0 – 3 and at night for Days 4-21 as directed by the Post-Procedure Care Instructions?							 YES  NO				

APPENDIX C: SUBJECT TAKE HOME POST-PROCEDURE CARE INSTRUCTIONS

Compression Garment Instructions:

It is important to wear the compression garment following your study procedure as directed by these instructions. This is an important part of the healing process.

- **Days 0-3:** Wear the neck compression garment for 22 hours per day, removing only for showering/bathing.
- **Days 4-21:** Wear the neck compression garment at night.

Additional Instructions:

- Complete Subject Diary daily through your 14-Day Follow-up Visit.
- Report any treatment effects by noting them in the Subject Diary.
- Call the investigator or study staff if you have a complication outside of the Expected Treatment Effects listed in the Subject Diary.
- Bring your Subject Diary in with you to each visit, through the 14-Day Follow-up Visit when you will turn the Subject Diary into study staff.
- Continue to keep your study doctor and/or study staff aware of any new complications you may experience beyond the 14-Day Follow-up Visit.

Follow-up Visits & Subject Contact outside of Follow-up Visits

You will be asked to return to the study site at the following times post-procedure:

- 1 (+2) day
- 7 (± 1) days
- 14 (± 3) days
- 30 (± 7) days
- 90 (± 10) days
- 180 (± 15) days

Your study doctor may ask you to come into the office if you are experiencing a complication. As well, study staff will contact you if you have an ongoing Expected Treatment Effect or complication at the following time points, as applicable:

- 21 (± 5) days
- 45 (± 5) days
- 60 (± 5) days
- 75 (± 5) days
- 105 (± 5) days
- 120 (± 5) days
- 135 (± 5) days
- 150 (± 5) days
- 165 (± 5) days

APPENDIX D: VALIDATED ASSESSMENT SCALE FOR PLATYSMAL BANDS²⁴

FDA	Food and Drug Administration
GAIS	Global Aesthetic Improvement Scale
GCP	Good Clinical Practice
ICH	International Conference for Harmonization of Technical Requirements of Pharmaceuticals for Human Use
IPR	Independent Photographic Reviewer
IRB	Institutional Review Board
ITT	Intent-to-Treat
MDD	Medical Device Directive
mITT	Modified Intent-to-Treat
NRS	Numeric Rating Scale
NSAID	Non-Steroidal Anti-Inflammatory Drug
PP	Per Protocol
PPS	Per Protocol Set
PR-(S)AE	Procedure-Related (Serious) Adverse Event
RF	Radiofrequency
SAE	Serious Adverse Event
SAP	Statistical Analysis Plan
UADE	Unanticipated Adverse Device Effect

1 PURPOSE

The purpose of this Statistical Analysis Plan (SAP) is to document the statistical design considerations for the study of a new medical device, the Renuvion APR device to improve the appearance of lax tissue in the neck and submental regions. This SAP documents the sample size estimation, study objectives, endpoints, data collection tools, and analysis plan. The requirements of the United States FDA and European MDD have been considered in the development of this document.

Once the study is completed a 510(k) will be submitted to the agency to request expanding the indications of the Renuvion APR (cleared under K191542).

Note: For marketing reasons that do not affect the safety and effectiveness of the device, we have updated the name from Apyx Plasma/RF to Renuvion APR handpiece. (APR stands for Apyx Plasma/RF).

2 REFERENCE DOCUMENTS

This SAP corresponds to the Apyx Clinical Investigation Protocol (CIP), “A Prospective, Multi-Center, Evaluator-Blinded Study Evaluating the Safety and Effectiveness of the Renuvion APR Device to Improve the Appearance of Lax Tissue in the Neck and Submental Region”, Protocol # VP-1902. Because detailed clinical information is included in the study protocol, the clinical aspects are *not* repeated in this SAP document. The information included in this SAP relates to the study design and data analysis.

3 OVERVIEW OF STATISTICAL DESIGN

This is a multi-center, single arm, single-blind (evaluator) prospective study of subjects who are seeking a procedure to reduce the appearance of laxity of the neck and submental regions at up to 8 investigational centers in the United States, with a maximum of 20 study subjects enrolled at each site.

Phase I (n=17) of this study was conducted and provided to the FDA as an interim safety report of safety data including information related to adverse events followed through resolution for all subjects. Phase I of this study was conducted prior to Revision 9 of the study protocol.

Phase II (n=65) of this study will be conducted as the pivotal study to demonstrate the safety and effectiveness of the Renuvion APR Device to improve the appearance of lax tissue in the neck and submental region. Phase II of the study begins with Revision 9 of the study protocol.

Study subjects that meet study eligibility criteria and have provided informed consent will be enrolled in the study. During the procedure, the investigators will use the Renuvion APR handpiece on the neck and submental areas of study subjects with the goal of reducing skin laxity.

Study subjects will be followed immediately following the procedure, and at 1 day, 7 days, 14 days, 30 days, 90 days, and 180 days post-procedure for study assessments. Assessments of

endpoints will use standardized evaluation tools and blinded evaluators as applicable. This includes the use of an independent 3-member evaluation team to eliminate the bias that is likely inherent in the investigators' assessments.

Phase II study enrollment is expected to occur over 6-8 months. Imaging and study assessments will continue through 6 months post-procedure. Total Phase II study duration is expected to be approximately 14 months. The 510(k) application for the device will be submitted based on 180-day post-procedure results. However, this clinical trial will continue until all adverse events are resolved. At that time, the trial will be considered complete, the final results will be determined, and a final report will be prepared.

Table 1 below shows the required evaluations and the schedule on which they are to occur.

Statistical Analysis Plan for the Renuvion APR Study, VP-1902, Rev. No. 3

Table 1: Study Required Procedures

	Baseline/ Pre- Procedure Screening ¹	Procedure (Day 0)	1 Day	7 Days	14 Days	30 Days	90 Days	180 Days
			1-3 days	6-8 days	11-17 days	23-37 days	80-100 days	165-195 days
Informed Consent	X							
Assess Inclusion/Exclusion Criteria	X							
Urine Pregnancy Test ²	X	X						
Medical History	X							
General Physical Exam	X							
Review Medications	X		X	X	X	X	X	X
2D/3D Photographic Images ³	X ⁶	X ⁸		X	X	X	X	X
Numeric Rating Scale (11-point NRS) ⁴		X ⁷	X	X	X	X	X	X
Study Procedure		X						
Adverse Event Assessment		X	X	X	X	X	X	X
TEN Testing of Sensory Nerves		X	X	X	X	X	As Needed	As Needed
Examination of Facial Motor Nerves		X	X	X	X	X	As Needed	As Needed
Burn Depth Assessment		As Needed	As Needed	As Needed	As Needed	As Needed	As Needed	As Needed
Modified Global Aesthetic Improvement Scale (GAIS) ⁵							X	X
Subject Diary		X			X			
Subject Satisfaction Survey								X

¹ Pre-procedure Screening assessments to take place within 30 days prior to undergoing the procedure.

² Up to two urine pregnancy tests must be obtained prior to study procedure for females with child-bearing potential (one at pre-procedure screening and one on the day of the procedure prior to the procedure if screening and procedure are not performed on the same day).

³Digital photographs will be taken and labeled according to Photography Instructions. 2D images will be extracted from 3D imaging. Both 2D and 3D images will be used for quantitative assessments. Standard positioning and lighting will be used for all photographs.

⁴ To be completed by the study subject on a day of the procedure (prior to the procedure and immediately following the procedure) and at all follow-up visits.

⁵ To be completed by Investigator and study subject at day 90 and day 180 follow-up visits.

⁶ Grimace image taken in addition to standard images at Baseline only.

⁷ NRS pain score will be captured prior to study treatment and immediately (within 60 minutes) after procedure.

⁸ Pre-procedure images may be taken if Baseline/Screening images are not considered acceptable by the quality review team, however if the Baseline/Screening image is acceptable by the quality review team, no additional pre-procedure image needs to be taken.

4 STUDY OBJECTIVES AND ENDPOINTS

4.1 Primary Effectiveness Objective and Endpoint

The primary effectiveness endpoint is improvement in the appearance of lax tissue in the neck and submental region at 180-days as determined by qualitative 2D photography assessment by blinded Independent Photographic Reviewers.

The primary effectiveness objective is to demonstrate that the proportion of successful subjects exceeds the performance goal (PG).

$$H_0: P \leq PG \text{ vs } H_a: P > PG$$

Where P is the proportion of successful subjects and PG is the performance goal.

Three experienced, blinded photographic reviewers will perform a qualitative analysis/review of the pre-treatment and post-treatment sets of images of each subject in a blinded and randomized order. Each blinded reviewer will choose which image is the post-treatment image. Success of a subject will be the correct post-treatment image selection by at least 2 of the 3 reviewers. The percentage of subjects with successful post-treatment image selection will be calculated.

4.2 Primary Safety Objective and Endpoint

The primary safety endpoint is the level of pain and discomfort after treatment as reported by the subject on a Numeric Rating Scale (NRS) through the 1-week follow-up visit.

The primary safety objective is to demonstrate that the proportion of subjects with none-to-moderate pain exceeds the performance goal (PG).

$$H_0: P \leq PG \text{ vs } H_a: P > PG$$

Where P is the proportion of subjects with acceptable pain and PG is the performance goal.

4.3 Additional Endpoints

Other endpoints to be evaluated include:

1. The improvement in the appearance of lax tissue in the neck and submental region at 90 days compared to baseline as determined by qualitative 2D photography assessment by blinded Independent Photographic Reviewers.
2. Subject Modified Global Aesthetic Improvement Scale (GAIS) at 90-day and 180-day FUV.
3. Investigator Modified GAIS at 90-day and 180-day FUV.
4. Subject satisfaction with procedure recorded at the 180-day FUV.
5. Quantitative improvement in overall lift of the submental area at 180 days as determined by quantitative assessment based on 2D photography.
 - a) The analysis will describe the population of subjects who respond to treatment by achieving at least 20 mm² of lift of the submental region. Responders will be

determined based on change from baseline of area as measured by 2D photography in standard lighting conditions.

- b) For the quantitative assessment, fixed landmarks on the subject's face will be used to systematically place a horizontal line, including the point where the chin meets the neck and 35 mm beyond. At this point, a vertical line will be placed and the area of submental skin between the two lines will be calculated. An area reduction of more than 20 mm² will be considered to be an improvement.
- 6. Quantitative improvement in submental volume at 180-days as determined by quantitative assessment based on 3D photography.
- 7. The evaluation of adverse events up to the 180-day visit following treatment.
- 8. The evaluation of pain scores through the 30-day follow-up visit as reported by the subject on a Numeric Rating Scale (NRS).

5 EVALUATION TOOLS

The following evaluation tools will be used in this study:

- 2-Dimensional and 3-Dimensional Photography
- Independent Photographic Assessments
- Quantitative Assessment of Lift
- Quantitative Assessment of Volume
- Modified Global Aesthetic Improvement Scale (GAIS)
- Subject Satisfaction Survey
- Numeric Rating Scale (NRS) for pain
- Subject Diary
- Adverse Event Reporting
- TEN Testing of Sensory Nerves
- Examination of Facial Motor Nerves
- Burn Depth Assessment (Burn Adverse Events Only)

More information about the evaluation tools, including how to administer them, is included in the study protocol. The schedule on which they are administered is provided in **Table 1**.

6 ADVERSE EVENTS ASSESSMENT REPORTING

The definitions of adverse events (AEs) and the subtypes are provided in the study protocol. Adverse events will be classified by the investigator as to:

- Anticipated vs unanticipated
- Serious vs not serious
- Expected Treatment Effect (ETE) vs Adverse Event (AE)
- Severity: mild, moderate, severe
- Device causality: not related, related, undetermined
- Procedure causality: not related, related, undetermined.

7.1.2 Primary Safety Hypothesis Test

The sample size was also calculated for the primary safety hypothesis. Coincidentally, the parameters were identical to those for the primary effectiveness hypothesis, so the sample size was an identical test.

7.2 Performance Goal Rationale

7.2.1 Primary Effectiveness Hypothesis

A Performance Goal (PG) of 55% will be used for testing. A PG of 55% is clinically relevant to ensure that there are significant benefits of the procedure to outweigh its risk. The lower bound of the confidence interval of the proportion of subject achieving treatment successes will be compared against this Performance Goal. This primary effectiveness endpoint definition and performance

¹ PASS 2019 Power Analysis and Sample Size Software (2019). NCSS, LLC. Kaysville, Utah, USA, ness.com/software/pass.

goal is more conservative and supported by the results of the Ulthera System study that was conducted to support equivalent indications cleared under K121700. Moreover, this PG is supported by the hypothesis and results of the clinical studies conducted to support the following cleared devices and studies published in clinicaltrials.gov as summarized in **Table 3**.

Table 3: Performance Goal Support

Trial	Sample size	Successes	Success rate	Exact (Clopper-Pearson) ² 95% lower CI
Ulthera K121700.	70	43	61%	51%
Ulthera K134032	54	37	68%	57%
SofWave NCT04146584	112	56	50%	42%
Evolve System NCT04124419	20	14	70%	49%
COMBINED (weighted)	256	150	58%	48%
COMBINED (unweighted)	256	150	63%	50%

7.2.2 Primary Safety Hypothesis

A PG of 55% was also established for the primary safety hypothesis test. There were two parts to establishing the PG:

1. Determining which values on an 11-point NRS scale correspond to mild pain and which to moderate.
2. Determining what percentage of patients with no-to-moderate pain through 7-days is minimally acceptable for a cosmetic procedure.

The first part was answered by Boonstra et al (2016)³, who showed that on a 11-point NRS, cut-off points of 5 for mild pain and 7 for moderate pain were appropriate. The second part was answered by Broughton et al (2006)⁴, who estimated that approximately 55% of subjects reported no-to-moderate pain during the first week post-procedure.

The Broughton estimate was taken from Table 3 of the journal article (see **Table 4**), which tabulated the percentages of patients reporting pain levels following liposuction by time following the procedure and number of treatment areas. Using the data for subjects receiving treatment in 1-2 areas, we found that 53.4% of subjects reported no higher than moderate pain during the first week post-procedure:

² Clopper, C.; Pearson, E. S. (1934). "The use of confidence or fiducial limits illustrated in the case of the binomial". *Biometrika*. 26 (4): 404–413. doi:10.1093/biomet/26.4.404

³ Boonstra AM, Stewart RE, Koke AJA, et al. Cut-Off Points for Mild, Moderate, and Severe Pain on the Numeric Rating Scale for Pain in Patients with Chronic Musculoskeletal Pain: Variability and Influence of Sex and Catastrophizing. *Front Psychol* 2016; 7: 1466.

⁴ Broughton G II, Horton B, Kipschitz A, et al. Lifestyle Outcomes, Satisfaction, and Attitudes of Patients after Liposuction: A Dallas Experience. *Plast. Reconstr. Surg.* 2006; 117: 1738-1749.

Table 4: Exert of Table 3 Broughton article

Table 3: 1-2 Areas Liposuctioned

Discomfort Level by Final Report (per Subject)

	None	Mild	Moderate	Severe*	TOTAL
1 day	0.023	0.023			
2-3 days		0.093	0.047		
4-7 days		0.209	0.139	0.047	
TOTAL	0.023	0.325	0.186	0.047	.534
> 7 days*	0.023	0.093	0.093	0.209	0.418

* Gray cells not used in calculations.

Therefore, we set our PG at 55%. The null hypothesis test is that Renuvion APR results in fewer than 55% of subjects with maximal pain of “moderate” during the first week post-procedure (i.e., more than 45% have severe pain). The alternative is that more than 55% have moderate or less pain, and fewer than 45% have severe pain.

8 ANALYSIS POPULATIONS AND HANDLING MISSING DATA

8.1 Analysis Sets and Handling of Missing Data

8.1.1 Full Analysis Dataset

(Intent-to-Treat Sample, ITT)

The ITT sample will be used in the primary safety analysis. This is defined as the subjects who enrolled in the trial and on whom the procedure was initiated at least to the point where energy from Renuvion entered the subject’s skin.

8.1.2 Primary Modified Analysis Dataset

(Primary Modified Intent-to-Treat Sample, PmITT)

The PmITT sample will be used in the primary effectiveness analysis. Participants enrolled in the study who had baseline photographs taken, completed the study procedure, and have at least one post-treatment photograph at or between 90 and 180 days will be included in the ITT sample.

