6.3 Study Procedure

On the day of the procedure and prior to the study procedure, female subjects with child-bearing potential must complete a urine pregnancy test (result must be obtained prior to the procedure).

Medications at investigator discretion may be provided as follows:

- Optional for Procedure (given within 90 minutes prior to procedure):
 - Ativan 2mg or Valium 10-20mg
 - Norco 5-10mg, Hydrocodone 5-10mg, or Ultram 200mg

A responsible driver (friend or family member) is required if these medications are prescribed.

During the study procedure, subjects will be treated with the Renuvion APR device according to the product IFUs and procedures described in this section of the protocol. The bilateral treatment area includes the tissue of the neck (to the posterior border of the sternocleidomastoid muscle) and submental area. Treatment will be performed through three (3) incisions (2 periauricular and 1 submental) with each incision large enough to allow for gas egress, see **Figure 1**. Each incision site will be anesthetized with 1% or 2% Lidocaine with Epinephrine (1:100,000) prior to incision being made.

[figure not shown]

Figure 1: Treatment incisions (2 periauricular and 1 submental).

The treatment area will be infused with standard of care tumescent solution referred to as a Klein solution. The solution consists of 1% or 2% Lidocaine (Plain) to make a 0.2% concentration (double Klein) and Epinephrine 1mg/1ml (1:1,000) and optional Sodium Bicarbonate 8.4% added to Normal Saline or Lactated Ringers. Infuse area with 150-250cc or until the area is taut. To prevent lidocaine toxicity, 35-55mg/kg should not be exceeded¹⁶.

Once infused with Klein solution, undermining of the tissue in the area to be treated will be performed using a cannula 3-4mm in diameter. No energy (i.e. radiofrequency, ultra-sound, or laser energy) or suction will be used during the undermining of the tissue.

After undermining, the Renuvion APR device treatment will be performed using 4-6 treatment passes with settings of 70% power and 1.5 LPM of helium flow with an activation speed of approximately 1-3 cm/s. Prior to performing treatment through each one of the three (3) incisions, the investigator will evaluate activation speed by performing the following steps in the sterile field at a safe distance from the subject:

1. Using a sterile ruler, two parallel lines will be drawn in the sterile field that are 10cm apart.

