10.4 Device Malfunction/Observations

All malfunctions of, or defects of the delivery system will be recorded on the Device Malfunction/Observation Case Report Form and reported to the Sponsor by the investigational sites. This will include situations where the delivery system did not perform as intended; user errors; study device/component being physically defective, including out of the box failure.

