8.1.5 Imputation of Missing Values

Those with missing post-treatment photographs at the 180-day visit will have their last post-treatment photograph (such as the 90-day follow-up image) carried forward for use in the IPR assessment for the primary effectiveness endpoint. Since generally the appearance of lax tissue in the neck and submental regions will continue to improve for up to 180 days post-procedure, post-treatment photographs taken at a time point earlier than the 180-day visit will not show more improvement than the missing 180-day photographs. Therefore, the last-value-carried-forward (LVCF) imputation is conservative.

For those subjects with missing primary endpoint data at the 180-day visit and no follow-up images available to carry-forward, the primary effectiveness objective will have the missing data multiply imputed using the patient's baseline characteristics and follow-up evaluations before and after the missing data.

The primary effectiveness hypothesis test will use this data set with a combination of LVCF and multiply imputed values carried out on the PmITT analysis set.

Those with missing endpoint data at the 7-day FUV for the primary safety objective will have the missing data multiply imputed using the patient's baseline characteristics and follow-up evaluations before and after the missing data. The primary safety hypothesis test will use this data set carried out on the ITT analysis set.

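### The primary effectiveness set admits only subjects with a completed procedure, so a subject who received Renuvion energy but was stopped early is left out of the primary test even with scorable photographs

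*SAP*

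**What the plan says.** SAP 8.1.2 states: "The PmITT sample will be used in the primary effectiveness analysis". It admits "Participants enrolled in the study who had baseline photographs taken, completed the study procedure, and have at least one post-treatment photograph" in the day 90 to 180 window. Completion is thus an entry condition separate from the photographs. (The section's closing words name the ITT sample, but its heading and first sentence show that PmITT is meant.)

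SAP 8.1.1 uses a different entry point, namely subjects "on whom the procedure was initiated at least to the point where energy from Renuvion entered" the skin, and adds: "The ITT sample will be used in the primary safety analysis". The SAP itself therefore separates a started procedure from a completed one.

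The other sections bearing on this are:

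- SAP 8.1.3: the SmITT sets, for secondary and additional analyses, need baseline and endpoint data only. They carry no completion condition.
- SAP 8.1.4: the per-protocol set is a subset of PmITT.
- SAP 8.1.5: "The primary effectiveness hypothesis test will use this data set with a combination of LVCF and multiply imputed values carried out on the PmITT analysis".
- SAP 8.1.7: the tipping-point analysis changes imputed values only.
- SAP 8.1.8: reasons for exclusion are examined and reported. No outcome is assigned.

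Neither document defines completion. Protocol 6.3 says "Treatment will be performed through three (3) incisions (2 periauricular and 1 submental"), with 4-6 passes. Protocol 10.4 has a form for malfunctions: "This will include situations where the delivery system did not perform as intended; user errors".

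**The concern.** Suppose treatment is stopped after one of the three incisions. Protocol 9.2 lists burns, gas buildup and bleeding among the risks, and Protocol 10.4 foresees malfunctions. The subject has been exposed and counts for safety. The day-180 photographs are still scheduled and could be read by the blinded reviewers. Under SAP 8.1.2 the subject is nevertheless outside the primary effectiveness test.

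The reason for exclusion arises after exposure and may be related to the device. In a single arm tested against a fixed 55% goal, no comparator offsets such a selection. The estimate then describes completed treatments, whereas the stated objective concerns subjects treated with the device. Because completion is undefined, the decision on who counts can also be taken late and by judgement.

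**Working it through.** **Inputs from the documents.** Performance goal 0.55, assumed success rate 0.75, one-sided alpha 0.025, exact binomial test, N = 60, reject at 41 or more, 65 treated (SAP 7.1.1 and its Table 2). Success means at least 2 of 3 reviewers correct (SAP 4.1).

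**Assumptions.** k = 1 to 3 of 65 procedures stopped early, since the documents give no figure. The success rate q of stopped subjects is unknown; three values are used: 0 (all fail), 0.5 (reviewers guess) and 0.75 (same as completers).

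**Step 1, the plan's own figure.** P(X ≥ 41 | 60, 0.75) = 0.90752, which matches Table 2. P(X ≥ 41 | 60, 0.55) = 0.0246, within alpha.

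**Step 2, the guess rate.** With three independent guesses, P(at least 2 correct) = 3(0.5)³ + (0.5)³ = 0.5.

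**Step 3, overstatement of the rate.** Completers at 75%, minus the all-treated rate:

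0.75 − [(65 − k)(0.75) + kq]/65 = k(0.75 − q)/65

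| k | q = 0 | q = 0.5 | q = 0.75 |
|---|---|---|---|
| 1 | 1.2 points | 0.4 | 0 |
| 2 | 2.3 | 0.8 | 0 |
| 3 | 3.5 | 1.2 | 0 |

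**Step 4, the boundary case.** One stopped subject is added to a just-passing result (p0 = 0.55):

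- 41/60: p = 0.0246, met.
- 41/61 (added subject is a non-success): p = 0.0356, not met; 42 needed.
- 42/61 (added subject is a success): p = 0.0192, met.

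**Step 5, chance of a false pass.** Let the true all-treated rate be exactly 55%. The completers' rate is then (65 × 0.55 − kq)/(65 − k), tested at the exact threshold for n = 65 − k.

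| k | Threshold | Completers' rate, q = 0 | False pass | Completers' rate, q = 0.5 | False pass |
|---|---|---|---|---|---|
| 1 | 44/64 | 0.5586 | 2.4% | 0.5508 | 1.8% |
| 2 | 43/63 | 0.5675 | 4.2% | 0.5516 | 2.4% |
| 3 | 43/62 | 0.5766 | 4.0% | 0.5524 | 1.6% |

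With all 65 counted at a uniform 55% (threshold 45), the figure is 1.4%. Some of the variation between rows comes from the discreteness of the exact test.

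**The case against.** The case for leaving the text alone has five parts.

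- **These subjects are not lost to every effectiveness analysis.** This stands. A reader might infer that no effectiveness analysis includes them, but SAP 8.1.3 contradicts that. They can enter the descriptive endpoints, including the 90-day photographic review, which SAP Table 5 treats as the primary endpoint at an earlier time. The gap is confined to the primary test, its tipping-point analysis and the per-protocol set.
- **Upward bias is not certain.** This stands. It requires partly treated subjects to succeed less often than completers. That is plausible with less tissue treated, but Protocol 6.3 has the area undermined before any energy is applied, so they are not untreated. Nor is every early stop caused by the device: Protocol 10.4 also covers user errors, and it does not mention stopping a procedure.
- **Counting each such subject as a failure exaggerates the effect.** This stands. If their images are read, guessing alone gives 50%, and the false-pass chance for k = 1 to 3 stays below 2.5%. The reversal in step 4 also needs a result of exactly 41/60. At a 75% true rate that has probability 0.9075 − 0.8514 = 5.6%, and half of that, about 2.8%, if the added subject scores at 50%.
- **Exclusions are disclosed under SAP 8.1.8.** This is true and helpful, but a reported reason is not an outcome in the test.
- **Protocol 5.2 already defines enrolled subjects as having undergone the procedure.** This does not settle the matter. SAP 8.1.1 adds initiation to enrolment and 8.1.2 adds completion. Neither condition would be needed if enrolment meant completion.

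**Conclusion.** The concern holds. Followed as written, SAP 8.1.2 removes energy-exposed subjects from the primary effectiveness test because of a post-exposure event, and nothing in 8.1.4, 8.1.5, 8.1.7 or 8.1.8 brings them back to that test. The bias is expected to be upward, on the condition that partly treated subjects do worse than completers.

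For the assumed 1 to 3 stopped procedures the overstatement is 0.4 to 1.2 points at the guess rate and 1.2 to 3.5 points in the worst case. It is zero if none is stopped. A false-pass chance above 2.5% appears in this range only if all stopped subjects would fail and there are two or three of them.

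A reader might conclude that one excluded subject would overturn the trial. The documents do not support that: it needs both a result on the threshold and a non-success in the added subject. This is a definite but probably small defect, worth correcting because the correction is cheap and the result could be borderline.

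**What to change.** 1. In SAP 8.1.2, replace the completion condition with the 8.1.1 criterion, that the "procedure was initiated at least to the point where energy from Renuvion entered" the subject's skin. Photographs of subjects with an incomplete procedure are then read and scored by the blinded reviewers like all others, with no automatic failure.
2. Move completion to the per-protocol definition in SAP 8.1.4, with an objective definition based on procedure data already recorded and fixed before any unblinded review of results.
3. Correct the closing words of SAP 8.1.2 so that they name the PmITT sample.

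The cost is SAP wording only; the visits and photographs are already scheduled. The observed success rate may be slightly lower. The photograph condition in 8.1.2 is untouched, so a stopped subject who never returns for images stays outside the set. That condition also sits uneasily with 8.1.5, which imputes for subjects without any follow-up image, and should be reconciled separately.
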